1.3 Prostate Specific Membrane Antigen (PSMA)

PSMA, also known as folate hydrolase I or glutamate carboxypeptidase II, is a 750-amino acid type II transmembrane glycoprotein expressed in normal human prostate epithelium. PSMA is over-expressed in virtually all prostate cancers and its expression is increased in poorly differentiated, metastatic and castration-refractory carcinomas (25, 26). The expression of PSMA in non-prostate tissues is predominantly within the small intestine, proximal renal tubules and salivary glands. However, in these tissues, it is expressed at levels 100-1000 times less than in prostate tissue (27, 28).

PSMA targeted imaging and therapy agents using small peptide ligands work by binding to an enzymatic binding site on the external component of the transmembrane receptor. Following the binding to the PSMA enzymatic site, the protein complex is internalised by endocytosis via clarithromycin coated pits with accumulation in endosomes and later released into the cytoplasm (29). This combination of high tumour specificity and internalisation following ligand binding makes the PSMA receptor an ideal target not only for imaging, but also for targeted therapeutics for prostate cancer.

The PSMA receptor has a complex role in the prostate cancer cell, functioning as a pro- proliferative agent, and is associated with the upregulation of both the phosphoinositide 3- kinase (PI3K) and protein kinase B (AKT) pathways (30). PSMA initiates signalling upstream of PI3K through G protein-coupled receptors, specifically via the metabotropic glutamate receptor. PSMA's carboxypeptidase activity releases glutamate from vitamin B9 and other glutamated substrates. The activated glutamate receptor subsequently induces activation of PI3K. Blocking the PSMA receptor in cell lines causes a significant involuntary response. This effect becomes even more marked when a PSMA blocker is used in conjunction with enzalutamide (30). Given the PSMA receptors intrinsic association with signal transduction pathways, such as Pi3K and Akt, that promotes survival and growth, it is possible that PSMA expression and particularly upregulation may be a trackable measure of cellular resistance to prostate cancer treatments, and particularly to androgen signalling inhibition.

1.4 PSMA Imaging

Existing and emerging data since 2015 in the use of PSMA PET has demonstrated high accuracy for the diagnosis of recurrent prostate cancer at early stages of disease, which changes both management and treatment outcomes (1, 3, 4, 6, 8, 31-35). Gallium-68 (^{68}Ga) PSMA-HBED-11 is a positron-emitting isotope that binds with high affinity to the PSMA receptor. ^{68}Ga -PSMA-PET/CT is more sensitive and specific for prostate cancer metastasis than conventional imaging (CT and 99- technetium bone scans) and is likely to emerge as a new standard of imaging in prostate cancer. A series of trials have validated its use in early prostate cancer (1, 3, 4, 8, 33, 35, 36). An analysis of 164 men who had PSMA PET triaged radiotherapy treatment for biochemical recurrence showed that the PSMA PET result was the strongest predictor of a treatment response to salvage radiotherapy – more so than other clinical predictors such as Gleason score / Grade Score, PSA

doubling time, PSA or seminal vesical involvement(8). A prospective multisite (PROPs trial) demonstrated that men with PSMA- positive disease outside of the prostate fossa have a poor response to targeted therapy, even when the radiotherapy fields are expanded to include all sites of disease(7). However, to date, there is little information on the value of PSMA PET in the setting of metastatic disease, either for diagnosis or for prognosis.

While we know that PSMA PET has prognostic value in men with biochemical failure post radical prostatectomy, there is no information currently as to whether PSMA PET findings can predict whether individual men will respond to androgen signalling inhibition, or whether there is any association between PSMA PET parameters and other risk factors for poor response to androgen signalling inhibition, such as ARV7 splice variant expression. However, given the PSMA receptors role within the cell, it is possible that PSMA PET may be able to identify castrate resistant clones early, and accurately identify men at risk of early treatment failure with androgen signalling inhibition.

1.5 Lu-PSMA Targeted Therapy

¹⁷⁷Lu is a radionuclide isotope of the rare earth metal lutetium, which has an established therapeutic role as peptide receptor radionuclide therapy. ¹⁷⁷Lu has favourable physical characteristics as a therapeutic radiation payload, having both a short-range β particle (mean range: 1.5 mm) and a small amount of γ emission. In two published prospective trials (6, 10), Lu-PSMA therapy has been shown to be an effective, well tolerated treatment in men with mCRPC and those with progressive disease after chemotherapy has failed. Treatment response rates ranged between 36-56% reduction in PSA with mild toxicity profiles, the most common being a moderately dry mouth. Importantly, researchers have found a strong correlation between the intensity of PSMA PET avidity on screening and response to Lu-PSMA therapy (6). A minimum PET intensity score appears to be required to ensure a treatment response to PSMA targeted treatments. There are ongoing randomized trials evaluating the efficacy of this treatment relative to chemotherapy (cabazitaxel) and best supportive care (TheraP and VISION). A single arm prospective trial is assessing the value of combination treatment with Lu-PSMA and NOX66, a radiation sensitizer in men who have failed cabazitaxel chemotherapy. What has not yet been evaluated is if Lu-PSMA treatment has a role in earlier phase disease, and in whom and in what sequence or combination with other therapies the treatment would be most effective. Moreover, the implications of Lu-PSMA for health care resource use are not well understood – both in terms of the direct requirements for health care resources for the delivery of Lu-PSMA and the potential to influence downstream health care use in men who undergo Lu-PSMA therapy.

1.6 PSMA and Androgen Receptor Interaction

Previous cell line work has revealed an intriguing and potentially clinically useful inter-relationship between the androgen and PSMA receptors within prostate cancer cells. This appears to be a *bi-directional* effect, with androgen receptor blockade upregulating PSMA receptor expression, and PSMA receptor blockade in turn increasing the involutional response of tumour cells to enzalutamide (30). In contrast to PSA, PSMA expression on the prostate cancer cell surface has been reported to increase with androgen receptor inhibition *in vitro* (37-39). Evans *et al.* demonstrated that PSMA expression in mice bearing PSMA expressing xenografts is increased with both orchidectomy and enzalutamide (38). Hope et al confirmed that PSMA intensity increased significantly with androgen blockade in LNCaP-AR xenograft mouse models (40). An increase in mRNA level in PSMA was measured with anti-androgen treatment in castrate sensitive, castrate resistant and abiraterone tolerant castrate resistant cell lines (39). Upregulating PSMA receptor activity on the cell surface of prostate cancer cells in mice also has a direct effect in increasing the volumes of ⁶⁸Ga-PSMA that adheres to the cell surface of prostate cancer cells and that which is internalised into the cell (40).

The effect of this interaction *in vivo* in humans in fact appears more complex. A prospective imaging trial in men commencing androgen signalling inhibition therapy was undertaken measuring the effect of androgen blockade on PSMA PET findings (13). These men undertook serial imaging at baseline, day 9, day 18 and day 28, in addition to PSA/testosterone at all imaging time points after commencing androgen blockade. Eight men with hormone naïve prostate cancer and 7 men with mCRPC were imaged. This work showed that in the **hormone naïve** state, PSMA PET intensity **significantly reduces** with the introduction of androgen blockade. By contrast, men with **castration resistant disease** commencing on androgen signalling inhibition (enzalutamide or abiraterone) had a **significant increase** in PSMA intensity. All men with mCRPC showed an increase in PSMA PET intensity (SUV max and volume) by day 9, with a 45% median increase in PSMA SUV max on PET scans within 9 days of commencing enzalutamide in men with mCRPC. This increase in PSMA intensity persists up to 28 days after commencing enzalutamide, even when the PSA is falling (Figure 2).

[figure not shown]

Figure 3. Waterfall plot of treatment response of LNCaP-Ctrl xenografts. Mice received bilateral flank xenografts. Treatment was administered daily IV on day 24 after xenograft implantation (enzalutamide, 0.5 mg/kg; 2-PMPA, 20 mg/kg; Enz + 2-P, 0.5 mg/kg enzalutamide and 20 mg/kg 2-PMPA) PMPA = PSMA inhibitor (30)

1.7 Tumour Heterogeneity

A key challenge to the development of any personalized therapies is the intrinsic dynamism of multiple tumour clones that can evolve and acquire resistance with pressure selection. While the PSMA receptor is highly expressed in prostate cancer, with increasing expression in metastatic disease and with more aggressive tumour types, the expression of PSMA in prostate cancers is heterogeneous, particularly at the later stages of the disease. A study that assessed both primary and metastatic prostate cancer samples found that only 4% (2/51) primary tumours were PSMA negative, while 16% (8/51) of metastatic samples were PSMA negative or had low expression (42). An assessment of PSMA expression in circulating tumour cells (CTCs) from men with metastatic disease found significant variation in the ratio of PSMA positive and PSMA negative CTC levels between patients (43). This heterogeneity of PSMA expression has direct implications for the use of PSMA targeted therapy, and in the development of PSMA targeted therapy resistance. Recent work has shown that high uptake on PSMA PET is an important consideration for selecting men suitable for ¹⁷⁷Lu-PSMA therapy: between 15-30% of men will not be eligible for PSMA targeted treatment due to PSMA low or negative receptor expression. In the prospective study of Lu-PSMA undertaken at St Vincent's Hospital, Sydney, men who failed Lu-PSMA therapy had lower PSMA avidity on

screening images. No one with an SUV <15 on screening PSMA PET had a treatment response to Lu-PSMA therapy (6). This is an important consideration for Lu-PSMA therapy, especially if considering a therapy move to earlier stages of the prostate cancer journey, where PSMA intensity is often lower (it upregulates in castrate resistant disease). Hence, the concept of combining Lu-PSMA therapy with a therapeutic agent that also upregulates the PSMA receptor, is appealing. Early animal work has shown that incubating LNCaP cells with enzalutamide and lutetium-PSMA increases the lutetium entry into the cell more than incubating with Lu-PSMA alone (41).

1.8 Synergies of Combination Treatment

Enzalutamide is an effective hormonal treatment that has a demonstrated benefit on overall survival in men with metastatic prostate cancer. However, not all men respond to this form of treatment, and in some men the treatment can be short-lived (24). The reasons behind this resistance are likely to do with the development of castrate resistant clones related to somatic splice mutations of the androgen receptor. The concept of prolonging the effect of this well tolerated treatment by potentially reducing/eliminating these resistant clonal populations is the focus of this grant. Lu-PSMA therapy is proving to be an effective and well tolerated treatment in men with mCRPC and in whom progressive disease after chemotherapy has failed. The side effect profile from Lu-PSMA has little crossover with enzalutamide, suggesting that the combination should be well tolerated (unlike the combination of chemotherapy and Lu-PSMA, which would likely have significant toxicity disadvantages). Lu-PSMA has been administered (but not formally evaluated) with androgen signalling inhibition in subgroups in both the recent prospective studies undertaken by our research teams, with no increased toxicity, and also within the currently accruing VISION trial. The expected toxicities following Lu-PSMA relate to radiation damage to normal tissues that have PSMA expression, and in men with a high metastatic bone disease burden, bone marrow suppression. Early cell line and mouse work has demonstrated that the combination of a PSMA inhibitor given with enzalutamide to castrate resistant cell lines improved treatment response (30). Combination enzalutamide and Lu-PSMA in mouse xenografts increased cellular DNA damage compared to Lu-PSMA alone. In this small study, mouse survival was not prolonged, however, the authors culled the mice in the study early, limiting interpretation of this finding (37). Theoretically, combining enzalutamide with Lu-PSMA therapy may allow synergistic benefit, with the enzalutamide treating androgen signalling inhibitor sensitive clones, and the Lu-PSMA treating residual castrate resistant clones. A further mouse CRPC xenograft study evaluated the combination of enzalutamide and a PSMA blocker (PSMA ADC). This small study found that the combination of enzalutamide and PSMA ADC had a significantly higher tumour volume reduction compared to either enzalutamide or PSMA ADC given alone (44). Combination treatments may more effectively treat men with high rates of heterogeneity than single agent treatment alone.

1.9 Clinical Benefit of Measuring Circulating Tumour Cells (CTCs) in this Population

CTC assays for AR-V7 and CTC heterogeneity have been validated as biomarkers of resistance to AR-directed therapies and are accessible through a simple blood draw. These assays can provide results in less than a week and are globally deployable. Additionally, PSMA CTC assays have demonstrated pharmacodynamic changes with PSMA directed therapies that are associated with patient survival (43). Utilising CTCs as a diagnostic tool to both identify patients who will not respond to single agent AR-directed therapy, but who may respond to Lu-PSMA combination, can help to optimise patient therapy and improve patient survival. The development of a blood based PSMA CTC assay could further enhance and create an accessible diagnostic that complements PSMA-

directed PET imaging, which provides information on both level of expression and heterogeneity between metastatic tumour sites in individual patients.

Approximately 9% of mCRPC patients carry germline mutations (35, 36) and 18% carry somatic mutations in key DNA repair genes (BRCA1, BRCA2, ATM and CHEK2) (37). There is evidence that increased DNA repair activity is a feature of treatment resistant mCRPC (38), making expression levels of targetable DNA repair proteins ideal biomarkers of resistance. It is also likely that the frequency of mutations in DNA repair pathways increase as the patient progresses through treatment. CTCs and circulating tumour DNA (ctDNA) provide non-invasive avenues for analysing DNA aberrations and quantifying DNA repair transcripts or proteins that may have increased expression or activity. Determining the levels of DNA repair biomarkers in CTCs of responders and non-responders and assessing their correlation to evolving ctDNA mutations will enable us to further understand the mechanisms of resistance. At St. Vincent's Hospital we have reported a case of an exceptional responder to Lu-PSMA who harboured a BRCA2 mutation (in press JCO Precision Oncology) and are looking at the effect of DNA repair gene alterations in ctDNA on responses to Lu-PSMA. Further work through this study would allow us to better assess the significance of these mutations in predicting Lu-PSMA treatment response. Examining CTC transcripts would augment this work and determine if PARP, ATR, ATM or DNA-PK are valuable as new adjuvant treatment options using established small molecule inhibitors (39).

The emergence of Single-cell RNA sequencing (scRNA-Seq) has initiated a scientific revolution, driven by the study of individual cells, in our understanding of cell identity, diversity, development and function ((1). It has the power to provide a previously inaccessible degree of resolution to the characterisation of malignant subsets with considerable data demonstrating the feasibility and utility of single cell technologies to advance knowledge of human cancer biology (4- – 6).) ScRNA-Seq, has identified Hedgehog signalling to CAFs as a novel mediator of cancer stem cell plasticity and demonstrated the first clinical benefit from a CAF-directed therapy in patients with metastatic triple negative breast cancer (Phase I clinical trial EDALINE; Identifier NCT02027376).The data reveal cellular subsets in remarkable detail and highlight the complexity of the tumour heterogeneity.

Precision medicine is the concept of targeting the right patient for the right treatment at the right time. ENZA-p is a patient-centric proposal that aims to use new theranostic agents to do exactly that: to allow both more accurate prognostic decision making, and more effective personalised treatment with fewer side effects, for men confronting a potentially lethal condition. This trial aims to show that treating men with mCRPC with rational treatment combinations will improve treatment responses and delay the need for more toxic treatments. The study then aims to take the concept of precision medicine further by working on ways to best predict which men would best benefit from the combined treatment, and methods the cancer develops to become resistant to these treatments. We believe that developing synergistic complementary non-toxic combinations of drugs that work better together earlier, and then targeting treatments to the men who will best respond, will give men with a lethal disease the highest quality of life for the longest possible time. Moreover, it will ensure that we are making the best use of our limited health care resources; achieving maximal benefit for the individual patient and an efficient use of societal resources.

2 AIM AND OBJECTIVES

Aim	To determine the activity and safety of adding Lu-PSMA to enzalutamide in mCRPC not previously treated with chemotherapy; and to identify potential prognostic and predictive biomarkers from imaging, blood, and tissue.
Objectives	To determine the effects of treatment on:
Primary	1. PSA Progression Free Survival (PFS, PCWG3)
Secondary	2. Radiological PFS (RECIST 1.1 and PCWG3)
	3. PSA response rate (PSA reduction of $\geq 50\%$ from baseline)
	4. Pain response and PFS (PPI scale)
	5. Clinical PFS (imaging, symptoms, initiation of new anticancer treatment)
	6. Aspects of health-related quality of life (EORTC QLQ-C30, Patient DATA Form, Fear of Cancer Progression)
	7. Frequency and severity of adverse events (CTCAE v 5.0)
Tertiary	8. Overall survival (death from any cause)
	9. Resource use and incremental cost-effectiveness
	10. To identify biomarkers from imaging, blood, and tissue associated with prognosis, response to treatment, and/or safety, including:
	i) ^{68}Ga -PSMA PET/CT intensity up-regulation at baseline, Day 15, Day 92 and at first progression (PSA or radiological)
	ii) Associations between quantitative ^{68}Ga -PSMA PET/CT parameters (including ^{68}Ga -PSMA PET avidity) and outcomes
	iii) Associations between ^{68}Ga -PSMA PET avidity to other predictive biomarkers in mCRPC (baseline characteristics, FDG PET/CT, CTC, AR-V7)
	iv) Associations between clinical outcomes and other prognostic and/or predictive biomarkers (tissue and circulating), including circulating tumour cells (CTCs) and circulating tumour DNA (ctDNA)

3 DESIGN

Randomised, phase 2, stratified, multicentre, open label clinical trial.

Participants will be randomised to enzalutamide or enzalutamide and Lu-PSMA in a 1:1 ratio. A minimisation approach will be used to minimise chance imbalances across the following stratification factors: study site, volume of disease (>20 versus ≤ 20 sites of disease measured on ^{68}Ga -PSMA PET/CT), prior treatment with early docetaxel for castration-sensitive disease (yes vs no), and prior treatment with abiraterone (yes vs no).

4 STUDY POPULATION

Patients must meet all of the inclusion criteria and none of the exclusion criteria to be eligible for this trial. No exceptions will be made to these eligibility requirements at the time of registration. All

enquiries about eligibility should be addressed by contacting the NHMRC Clinical Trials Centre prior to registration.

4.1 Target Population

Men with mCRPC not previously treated with docetaxel for castration-resistant disease, suitable for treatment with enzalutamide and Lu-PSMA.

4.2 Inclusion Criteria

1. Males aged 18 or older with metastatic adenocarcinoma of the prostate defined by:
 - Documented histopathology of prostate adenocarcinoma (no features of neuroendocrine carcinoma)
 - OR
 - Metastatic disease typical of prostate cancer
2. Castration-resistant prostate cancer (defined as disease progressing despite castration by orchectomy or ongoing luteinising hormone-releasing hormone agonist or antagonist).
3. Progressive disease with rising PSA defined by PCWG3 criteria (sequence of 2 rising values at a minimum of 1-week intervals) AND $\text{PSA} \geq 5 \text{ ng/mL}$.
4. At least 2 of the following risk factors for early treatment failure with enzalutamide:
 - i. $\text{LDH} \geq \text{ULN}$
 - ii. $\text{ALP} \geq \text{ULN}$
 - iii. $\text{Albumin} < 35 \text{ g/L}$
 - iv. De novo metastatic disease (M1) at initial diagnosis *
 - v. < 3 years since initial diagnosis
 - vi. > 5 bone metastases *
 - vii. Visceral metastases *
 - viii. PSA doubling time < 84 days
 - ix. Pain requiring opiates for > 14 days
 - x. Prior treatment with abiraterone
- * Based on conventional imaging (CT and/or bone scan)
5. Target or non-target lesions according to RECIST 1.1 (Appendix 1) or PCWG3 (Appendix 3)
6. Significant PSMA avidity on ^{68}Ga -PSMA PET/CT, defined as $\text{SUV}_{\text{max}} > 15$ at a single site (regardless of lesion size) and $\text{SUV}_{\text{max}} > 10$ at sites of disease $\geq 10\text{mm}$ (unless subject to factors explaining a lower uptake, e.g. respiratory motion, reconstruction artefact)
7. ECOG performance status 0-2 (Appendix 2)
8. Adequate renal function:
 - Creatinine clearance $\geq 40\text{mL/ min}$

9. Adequate liver function:
 - Bilirubin < 1.5 x upper limit of normal (ULN) (or if bilirubin is between 1.5 - 2x ULN, must have a normal conjugated bilirubin)
 - AST or ALT ≤ 2.0 x ULN (or ≤ 5.0 x ULN in the presence of liver metastases)
10. Adequate bone marrow function:
 - Platelets ≥ 100 x10⁹/L
 - Haemoglobin ≥ 90g/L (no red blood cell transfusion in last 4 weeks)
 - Neutrophils > 1.5 x10⁹/L
11. Estimated life expectancy > 12 weeks
12. Study treatment both planned and able to start within 21 days of randomisation
13. Willing and able to comply with all study requirements (including both treatments: enzalutamide and Lu-PSMA), and all required study assessments
14. Signed, written, informed consent

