5.1.3 Required Background Treatment

All participants are to receive ongoing background androgen deprivation therapy with a LHRH analog (LHRH agonist or antagonist) or surgical castration, as per standard of care. The choice of the LHRHA or surgical castration is at the discretion of the treating clinician.

Administration of the LHRHA should be according to the product information guide. Options include but are not restricted to: goserelin, leuprorelin, triptorelin, or degarelix.

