6 ASSESSMENT PLAN

6.1 Schedule of Assessments

Stage	Screening	Baseline	On study treatment	At First Progression (PSA or radiological) ¹ AND End of Treatment for reasons other than progression	After last dose of study treatment		
Timing	Within 28 days prior to randomisation	Within 7 days prior to randomisation	All participants Day 15, then 4 weekly (\pm 7 days) ⁸	\pm 7 days	42 days and 84 days after last dose of study treatment (\pm 7 days)	Until radiological progression (6 weekly \pm 7 days)	After radiological progression (12 weekly \pm 7 days)
Informed consent (including Medicare consent)	X						
Medical oncology assessment ²	X	X ⁹	X	X	X	X	
Blood tests ³	X	X ⁹	X	X	X	X	
PSA	X	X ⁹	X	X	X	X	
Translational research bloods ^{4a}		X ^{4b}	Day 92 only	At first progression only, before subsequent therapy ⁵			
⁶⁸ Ga-PSMA PET/CT	X		Days 15 and 92	X (At progression only) ⁵			
¹⁸ F FDG PET/CT	X			X (At progression only) ⁵			
SPECT CT			24hrs post Lu-PSMA				
CT CAP / Whole body bone scan ⁶	X		Day 99, then 12 weekly thereafter	X		12 weekly until radiological progression	
Tissue biopsy ^{4a}		Optional ^{4c}		Optional (At progression only) ⁵			
Adverse events ⁷			X	X	X		
Compliance			Days 15 and 43				
Concomitant medications				Within 30 days prior to an SAE			
HRQL forms		X ¹⁰	X (not day 15)	X	X	X	
Fear of Cancer Progression Short Form		X ¹⁰					
Survival and Subsequent Treatment					X	X	X

Notes

1. Refer to section 7.1 for definition of PSA progression or 7.2 for definition of Radiological progression.
2. Clinical assessment includes history (at baseline) and physical examination, performance status and weight. All visits after baseline include a review of any adverse events and physical examination as per standard of care for a participant at this stage of their disease and treatment
3. Blood tests include the following:
 - Haematology: Complete blood examination (CBE): haemoglobin concentration, white cell count, platelet count, white cell differential.
 - Biochemistry: Electrolytes, urea, creatinine (EUC); liver function tests (LFT): bilirubin, alkaline phosphatase (ALP), alanine aminotransferase (ALT), gamma glutamyl transferase (GGT), lactate dehydrogenase (LDH; screening only)
4. a. Refer to Biological Sampling Manual for details of collection, processing and shipping procedures.
b. Baseline TR blood draw after randomisation, within 7 days prior to commencing study treatment.

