The radiopharmacy within the nuclear medicine department at participating institutions will maintain a record of ^{177}Lu and PSMA (both PSMA-11 and PSMA-617) supply and use. A record will be maintained of the Lu-PSMA prepared for each participant. The radiopharmacy will also maintain a record of receipt and product destruction as appropriate. The oncology pharmacy will maintain a record of enzalutamide dispensed for each participant and subsequent returns. Enzalutamide compliance will be assessed at Day 15 and Day 43 (± 7 days). The oncology pharmacy will also maintain a record of drug receipt and drug destruction as appropriate. Participants will be asked to return unused drug and empty drug containers at each return visit. Drug accountability logs will be requested, as required, from each pharmacy for central review by each regional coordinating centre.

12.4 *Background treatment*

Androgen deprivation therapy will be provided according to usual practice. Drug accountability will not be performed for androgen deprivation therapy.

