13 STATISTICAL CONSIDERATIONS

13.1 Sample Size

The study will randomise patients to the experimental combination of enzalutamide and Lu-PSMA versus enzalutamide alone in a 1:1 ratio. A sample size of 160 patients recruited over 12 months and followed until 150 events occurred (approximately another 18 months), provides 80% power at the two-sided 5% level of significance to detect a HR of 0.625 assuming a median PSA PFS of 5 months in the enzalutamide alone arm whilst allowing for non-adherence to assigned treatment in up to 2 participants.

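### Inclusion 2 requires castration but takes orchiectomy or an ongoing LHRH analogue as proof of it; no castrate testosterone is required or listed, so ineffective castration could go undetected

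*Protocol*

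**What the plan says.** **Eligibility.** Section 4.1 limits the target population to mCRPC. Section 4.2, inclusion 2, defines castration resistance as "defined as disease progressing despite castration by orchectomy or ongoing luteinising hormone-releasing hormone agonist or antagonist". Inclusion 3 adds "Progressive disease with rising PSA defined by PCWG3 criteria (sequence of 2 rising values at a minimum of 1-week intervals") together with a PSA of at least 5 ng/mL. No exclusion criterion in section 4.3 concerns testosterone, and the PCWG3 extract in Appendix 3 contains no testosterone rule for entry.

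**Scheduled bloods.** Section 6.1, note 3, lists haematology and the following biochemistry: "Electrolytes, urea, creatinine (EUC); liver function tests (LFT): bilirubin, alkaline phosphatase (ALP), alanine aminotransferase (ALT), gamma glutamyl transferase (GGT), lactate dehydrogenase (LDH; screening only"). PSA has its own row in the schedule. Testosterone is not listed at any visit.

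**Background castration.** Section 5 requires androgen deprivation to be continuous and makes intermittent use a protocol violation. Section 5.1.3 states: "All participants are to receive ongoing background androgen deprivation therapy with a LHRH analog (LHRH agonist or antagonist) or surgical castration". It also asks that the analogue be given according to its product information. Section 12.4 states: "Drug accountability will not be performed for androgen deprivation therapy".

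**The only mention of testosterone.** Section 1.6 describes an earlier imaging study in which men had serial scans "in addition to PSA/testosterone at all imaging time points after commencing androgen blockade". That is background, not a procedure of this trial.

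**The concern.** Inclusion 2 names the state (castration) and the means (surgery or an ongoing analogue), but nothing checks that the means has produced the state. A man on an analogue that is not suppressing testosterone can have a rising PSA for that reason. On paper he meets inclusions 2 and 3.

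Three parts of the trial depend on the mCRPC label:

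- **The population.** The conclusion is meant for castration-resistant disease.
- **The primary comparison.** Section 13.1 assumes a median PSA PFS of 5 months on enzalutamide alone. Men who are not castration-resistant may progress at a different rate and may have a different treatment effect.
- **The Day 15 PSMA PET.** Section 1.6 reports that PSMA intensity fell with androgen blockade in hormone-naive men and rose in castration-resistant men. Tertiary objective 10(i) studies that up-regulation, so uncertain castration status adds noise to it.

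**Working it through.** **1. Does any rule measure castration?**

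| Place | What it controls | Does it check the hormone level? |
|---|---|---|
| 4.2, inclusion 2 | Method of castration, plus progression | No |
| 4.2, inclusion 3 | Rising PSA and PSA of at least 5 ng/mL | No |
| 6.1, note 3 | Haematology, biochemistry, LDH at screening | Testosterone not listed |
| 5 and 5.1.3 | Continuous ADT, given per product information | No |
| 12.4 | Accountability for ADT | Waived |

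Sections 5 and 5.1.3 deal by rule with a late or missed depot. They do not deal with a depot that is given on time and does not work.

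**2. The plan's own event number.** Section 13.1 says that the design "provides 80% power at the two-sided 5% level of significance to detect a HR of 0.625 assuming a median PSA PFS of 5 months" on enzalutamide alone, with 160 men, 150 events and non-adherence in up to 2 men.

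- Freedman: (1.96 + 0.842)² × [(1 + 0.625)/(1 − 0.625)]² = 7.85 × 18.78, which gives 148 events. With the allowance: 148/(1 − 2/160)² = 148/0.975, about 152.
- Schoenfeld: 4 × 7.85/(ln 0.625)² = 31.4/0.221, which gives 143 events. With the allowance: 143/0.975, about 147.
- Events expected by month 30, with exponential medians of 5 and 5/0.625 = 8 months and uniform accrual over 12 months: 76.8 + 69.5 = 146.3.

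The stated 150 events reproduce and are not in dispute.

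**3. Illustration of what misclassified men could do.** The documents give no inputs here, so these are all assumptions:

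- Share of men not castrate: 2%, 5% or 10% of 160, which is 0.02 × 160 = 3.2, 0.05 × 160 = 8 or 0.10 × 160 = 16 men.
- Their control median: 11 or 14.5 months (figures that section 1.2 gives for other groups, borrowed as stand-ins) or 24 months (no source).
- Their hazard ratio: 0.625, as in everyone else, or 1.

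The log-rank test was simulated at the 150th event. There were 3,000 runs for the base case and 2,000 for each other case. The simulation error is about √(0.8 × 0.2/2000) = 0.9 percentage points.

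| Assumed share | Power, HR 0.625 in them | Power, HR 1 in them | Median time to 150th event |
|---|---|---|---|
| 0% | 81% | not applicable | 32.5 months |
| 2% | 79-81% | 78-80% | 33-34 months |
| 5% | 73-79% | 69-74% | 34-37 months |
| 10% | 68-77% | 58-67% | 34-42 months |

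At 2% the loss is small and close to simulation error. It becomes material only from about 5%. Both the share and the outcomes behind it are assumed.

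**The case against.** The strongest reply is that inclusion 2 already demands progression despite castration. A man known not to be castrate fails it, a man after orchiectomy cannot miss a depot, and continuous ADT is enforced as a matter of protocol compliance. The protocol contradicts none of its own figures or rules. All of this stands. What remains is narrower: castration is required but not verified, so a man with unrecognised ineffective suppression could enter.

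Several stronger readings are tempting, and the documents do not support them:

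- **That note 3 is a complete list, so testosterone is certainly never drawn.** The note says only that the bloods include those items. It omits albumin, which inclusion 4(iii) uses, and AST, which inclusion 9 names. It shows that testosterone is not listed or required, and no more.
- **That non-castrate men would show falling PSMA intensity at Day 15.** Section 1.6 rests on 8 hormone-naive men and 7 men with mCRPC. A man already on an analogue with incomplete suppression belongs to neither group, and the documents have no data on him.
- **That his PSA would fall because castration is restored.** No passage provides for detecting or restoring it, and his response to enzalutamide is not documented.
- **That the arms are biased against each other.** Allocation is 1:1, so such men fall in both arms by chance.
- **That a margin of 160 − 150 = 10 event-free men would be used up.** The 150 events trigger the analysis, so slower events lengthen follow-up. PSA progression is also counted from the nadir (section 7.1), so an early fall does not make a man event-free.

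**Conclusion.** The point holds as a gap in verification. Inclusion 2 accepts the method of castration as evidence of its effect, no castrate testosterone is required or listed, and no other provision measures it. Men with ineffective castration could therefore be randomised and analysed as mCRPC without anyone knowing.

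The size cannot be established from the documents. Under the stated assumptions, power goes from 81% to about 78-81% at 2% misclassified and to about 69-79% at 5%. The low end at 5% also assumes no treatment effect and a 24-month control median in these men. The consequences are a less well-defined population, slower events, possible dilution of the primary effect and noise in a tertiary imaging analysis. A reader should not infer that the trial's comparison is invalid or that the event number is wrong. Eligibility and scheduled bloods are fixed by the protocol, so a statistical analysis plan could not close this gap. The change is worth making because it is cheap and protects the definition on which the question rests.

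**What to change.** - **Section 4.2, inclusion 2:** add a requirement that serum testosterone at screening is in the castrate range, with the numerical limit set by the sponsor.
- **Section 6.1, note 3:** add testosterone (screening only) beside LDH.

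The sample size and the analysis need no change. The cost is one routine local assay on a blood draw that is already scheduled. The downside is that a few men's registration may be delayed or declined.
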